PIS Participant Information Sheet

PMG Programme Management Group
PPI Patient and Public Involvment

PR Pulmonary Rehabilitation

PSC Programme Steering Committee

QALY Quality Adjusted Year Life

QC Quality Control

RCT Randomised Control Trial
REC Research Ethics Committee

SAE Serious Adverse Event SDV Source Data Verification

SOP Standard Operating Procedure

TMF Trial Master File

TMG Trial Management Group
TSC Trial Steering Committee

WP Work Package

KEY WORDS

Multimorbidity, multiple long-term conditions, rehabilitaition, randomised controlled trial, feasibility study

TRIAL SUMMARY

| Trial Title | Personalised Exercise-Rehabilitation FOR people with Multiple long-term conditions (multi-morbidity) PERFORM: Feasibility Study | | |
|----------------------|---|--|--|
| Trial Design | A 2-group parallel randomised feasibility study with embedded process and economic evaluations. Participants will be randomised to intervention (PERFORM rehabilitation programme + usual care) or control (usual care alone) | | |
| Trial Participants | People with two or more long term conditions (LTCs) at least one of which has evidence of benefit from an exercise-based intervention | | |
| Planned Sample Size | 60 participants with 2:1 intervention/control randomisation to intervention or control to be recruited across foursites. | | |
| Follow up duration | 3-months post randomisation. | | |
| | 4 month post randomisation maintenance session | | |
| | 6 month post randomisation | maintenance session | |
| Planned Trial Period | Start date: June 2023 | | |
| | End Date: June 2024 | | |
| Overarching aim | To assess the feasibility and PERFORM intervention and whether progression criteria warranted. | study methods and assess are achieved and full trial is | |
| | Objectives | Outcome Measures | |

| Co-primary feasibility objective(s) | To assess whether prespecified progression criteria are met to progress to the full randomised trial to assess clinical and costeffectiveness of the PERFORM intervention. | Progression criteria. • Percentage of target patients recruited in 4.5 months recruitment period • Retention at 3-months follow up • Intervention adherence (attendance of ≥60% of sessions) |
|-------------------------------------|--|---|
| Secondary feasibility objectives | To further refine the intervention and programme theory. | From process evaluation interviews |
| | To assess the feasibility and acceptability of data collection tools. | Proportion of patients with complete outcome data at 3-month follow up and process evaluation patient interviews |
| | To obtain estimates of key cost drivers. | From economic evaluation |
| | To assess risks of bias/contamination. | Outcome blinding breaks and access to PERFORM intervention by control group |

FUNDING AND SUPPORT IN KIND

FUNDER(S)

NIHR PGfAR NIHR202020

ROLE OF TRIAL SPONSOR

The Sponsor of this research is the University of Leicester. The University of Leicester is registered as a research sponsor with the Department of Health and routinely takes responsibility as sponsor for research activities within the NHS.

ROLES AND RESPONSIBILITIES OF TRIAL MANAGEMENT COMMITEES/GROUPS & INDIVIDUALS

Programme Management Group (PMG)

Monthly trial management meetings will take place, comprising the Chief Investigators, coapplicants, members of Leicester Clinical Trials Unit (LCTU) and a Patient Advisory Group (PAG) representative. These operational meetings will provide continuous monitoring of key milestones and provide a vehicle to highlight issues, and discuss and agree resolutions. In addition to these monthly meetings, the CIs/members of the research team will meet regularly with the LCTU hub to discuss the day to day running of the programme (these will be virtual). The PMG will report to the Programme Steering Committee (PSC).

Public Advisory Group (PAG)

The PAG, consisting of Patient and Public Involvement (PPI) representatives, will have 11 meetings as part of the larger PERFORM programme grant, each in Glasgow and Leicester to advise on overarching trial set-up, patient-facing materials and the topic guide for the semi-structured interviews and provide input to all WPs (plus 5 PAG evaluation/study meetings). The PAG would meet approximately every 6 months of the PERFORM programme grant timelines to provide input to all WPs, advise on trial conduct and dissemination of results. The PAG will report to the PMG (which will carry on after WP3 completion).

[figure not shown]
The PAG will evolve through the lifetime of the project and recruit new members (trial participants) to support PAG activities and dissemination events having first-hand experience of the intervention.

Programme Steering Committee (PSC)

A Programme Steering Committee (PSC) has been established to provide independent expert oversight of the PERFORM research programme and includes Trial Steering Committee (TSC) and Data Safety and Monitoring Committee (DSMC) responsibilities for WPs 3-5 (feasibility study and main trial). PSC meetings will normally take place once a year to provide overall supervision of the trial and ensure that the trial is conducted to the rigorous standards set out in the guidelines for good clinical practice; however the PSC may be convened during the recruitment phase of WP3 to advise/address any WP3 study concerns. The PSC consists of an independent chair, an independent statistician, other independent members who are experts in rehabilitation and multimorbidity, two patient representatives, meetings may also be attended by with PERFORM co-chief investigators, study manager, the sponsoring organisation, and representatives from the clinical research networks. The PSC will consider progression to full trial (WP4) following completion of the feasibility study (WP3). The PSC will make recommendations to the PMG and will report to the sponsor and the funder.

The routine reports reviewed by the PSC will include a summary of all SAEs. SAEs identified as related, life-threatening or resulting in death will be reported annually to the PSC members for review, unless requested more frequently by PSC. The decision regarding frequency of review may be re-evaluated by the PSC members throughout the study delivery, and then reported to the Sponsor for continuity in safety reporting.

TRIAL FLOW CHART

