3. TRIAL DESIGN

A parallel two group randomised feasibility study with nested process and economic evaluation. Patients will be randomly allocated to either intervention (PERFORM rehabilitation programme + usual care) or control (usual care alone). The feasibility study will be conducted across four sites with a total of 60 participants recruited over a 4.5 month period, with 40 participants randomised to the intervention group and 20 participants to the control group with a 3 month follow up after randomisation and a further 2 group maintenance sessions at 4 and 6 month post randomisation.

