7. INTERVENTION & CONTROL

7.1 Intervention group

The PERFORM rehabilitation programme will comprise an 8 week supervised rehabilitation programme, 6 weeks, twice weekly then 2 weeks, once a week that will be offered in either a primary or secondary care setting. Each session will last for 2 hours (1hr of 'move and improve

exercise sessions, and 1hr patient 'Health and Wellbeing' self care support session and Q&A/opportunity to interact with the group). The intervention will be offered within 4 weeks of randomisation.

The rehabilitation programme will comprise an exercise component with an accompanying education programme. The 'Health and Wellbeing' self care support sessions / educational package will offer advice and support for behaviour change to support positive lifestyle changes and symptom management. Much of the advice will be appropriate to all participants for example health eating, the benefits of exercise, stress management and relaxation techniques, medicines adherence, and exacerbation of symptoms. The aim of the education 'health and wellbeing' package is to support symptom management, risk factor management and enhance self-management skills. The education programme will be delivered by healthcare professionals delivered as informal and interactive sessions. The information will be supplemented by written leaflets and material to support the individual to share with their family and carers. After the 8 week programme the participant will have a discharge appointment in most cases this will take place 1-2 weeks following the last rehabilitation session.

Each 'move and improve' exercise session will offer an individually prescribed and progressed aerobic walking programme (a combination of walking (treadmill where available). In addition resistance training will be delivered that will be individually prescribed and progressed.

Participants will also be encouraged to complete a home exercise programme that will be closely monitored. A home exercise booklet will be provided as well as a progress tracker standardised exercise diary that will ask participants to record exercise frequency, duration and symptom scores post bout of exercise. This will be recorded for the aerobic and resistance programme.

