10.5 Interim analysis and criteria for the premature termination of the study

There are no formal criteria for stopping the study prematurely.

No interim analysis assessing the feasibility stop-go criteria with the possibility of early termination of the study is planned. However, due to the nature of the outcomes of recruitment and retention, these outcomes will be monitored along with serious adverse events throughout the study.

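### Annual SAE reporting to the PSC is the default, yet supervised exercise ends by about month 7, and no event-triggered route to the PSC is set

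*Protocol*

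**What the plan says.** Under the roles and responsibilities heading, the PSC is given both the steering and the data-monitoring functions for the feasibility study. On timing, the same section says that "PSC meetings will normally take place once a year to provide overall supervision of the trial" and that "SAEs identified as related, life-threatening or resulting in death will be reported annually to the PSC members for review". Two qualifications follow: the annual interval applies "unless requested more frequently by PSC", and "The decision regarding frequency of review may be re-evaluated by the PSC members throughout the study delivery". The PSC may also be convened during the recruitment phase if concerns arise. Its routine reports are to contain a summary of all SAEs.

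Elsewhere in the protocol:

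- Section 3: a "total of 60 participants recruited over a 4.5 month period", of whom 40 go to the intervention.
- Section 7.1: an 8-week supervised programme, and "The intervention will be offered within 4 weeks of randomisation".
- Section 6.13: only SAEs judged related to the programme or the study assessments are reported to and reviewed by the PSC and Sponsor. No timing is given.
- Section 6.13.1: related SAEs, from consent to the 3-month visit, go to the Sponsor within 24 hours. SUSARs go from the Sponsor to the ethics committee.
- Section 10.5: there are no formal stopping criteria. Of recruitment and retention it says that "these outcomes will be monitored along with serious adverse events throughout the study", without naming who does this.

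**The concern.** A yearly reporting cycle suits a trial that runs for several years. Here the supervised programme is finished for everyone in well under a year. If the default is followed, the committee charged with safety monitoring may first see the related, life-threatening or fatal events when no participant is still in supervised exercise. Its advice could then inform the main trial but could not protect anyone during the supervised programme of this one.

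The matter carries some weight because there are no formal stopping criteria, relatedness is judged by the site investigator, and section 6.9 notes that exercise risk is highest in people with existing cardiovascular disease. Coronary heart disease and heart failure are both qualifying conditions in section 5.1.

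**Working it through.** The protocol gives no figure for this interval, so the check is calendar arithmetic on its own inputs. One month is taken as 365.25 / 12 / 7 = 4.348 weeks, so 4 weeks = 0.92 months, 8 weeks = 1.84 months and 12 weeks = 2.76 months. Month 0 is the opening of recruitment.

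**Inputs.** Recruitment 4.5 months (section 3); start 0 to 4 weeks after randomisation and programme of 8 weeks (section 7.1); 3-month visit with a window of ±4 weeks (section 6.1); last maintenance session 6 months after randomisation (section 7.1); default PSC interval 12 months (PSC section).

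**Timeline for the last participant randomised.**

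| Event | Calculation | Month |
|---|---|---|
| Programme ends, immediate start | 4.5 + 1.84 | 6.3 |
| Programme ends, start at week 4 | 4.5 + 2.76 | 7.3 |
| 3-month visit, end of SAE reporting | 4.5 + 3 | 7.5 |
| Same, late edge of window | 4.5 + 3 + 0.92 | 8.4 |
| 6-month maintenance session | 4.5 + 6 | 10.5 |
| First annual report, if counted from month 0 | | 12 |

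Every event precedes a report counted from the opening of recruitment. The planned trial period, June 2023 to June 2024, is itself one reporting interval.

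**How likely is late review?** The protocol does not say when in the year the PSC report falls. As an illustration only, assume the date is uniformly distributed over 12 months. The chance that it misses the supervised period is:

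- 1 − 6.34/12 = 47% (immediate start)
- 1 − 7.26/12 = 40% (start at week 4)
- 1 − 10.5/12 = 12.5% if contact is counted to the last maintenance session

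Conversely, one report falls inside the supervised period with probability of about 53% to 60%.

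**What would the optional extra meeting catch?** It is named only for the recruitment phase, which closes at month 4.5. Assuming even recruitment, the share of intervention participants still to finish the programme at that point is 1.84/4.5 = 41% (immediate start) to 2.76/4.5 = 61% (start at week 4), or about 16 to 25 of 40.

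**Sensitivity to slow recruitment.** The last programme would run past month 12 only if recruitment lasted longer than 12 − 2.76 = 9.2 months, about twice the plan.

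**The case against.** Several points on the other side are sound.

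- A reader might infer that the PSC sees these SAEs only once a year. The text does not say that: the PSC can ask for more frequent reports, can revisit the frequency, and may be convened during recruitment.
- A reader might infer that the PSC is the only independent safeguard during the programme. It is not. Section 6.13.1 sends SUSARs to the ethics committee within 7 or 15 days, and section 6.14 requires notice of urgent safety measures within 3 days. The Sponsor also hears of related SAEs within 24 hours.
- A reader might infer that all 40 intervention participants will finish before any PSC review. That needs an annual date coinciding with the start of recruitment, which the protocol does not fix.
- The Programme Management Group meets monthly, can raise issues and reports to the PSC. Section 6.13 also provides for PSC review of related SAEs without an annual limit.
- The study is small, and section 6.9 describes the risk of harm from exercise as very low.

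What remains is narrower. Each route to the PSC is either discretionary or untimed. The PSC would have to ask about events that no rule puts before it. The management group consists largely of the investigators and trials-unit staff, and its stated task is milestones and operational issues. The ethics-committee route covers unexpected events, yet section 6.13 lets the PI and/or CI judge related injuries to be expected case by case. An event so classified would have neither that route nor a prompt route to the PSC.

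**Conclusion.** The point holds in a limited form. By default the PSC receives related, life-threatening or fatal SAEs yearly, and more often only at its own request. Supervised exercise ends at about month 6.3 to 7.3 and SAE reporting at about month 7.5 to 8.4, so PSC review can follow all supervised exercise, though it need not. The illustrative 40% to 47% rests on the assumed uniform annual date, and the timeline rests on recruitment finishing in 4.5 months. The documents do not support saying that late review is certain or that participants lack any independent protection meanwhile.

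A related inconsistency stands on its own. The PSC section promises a summary of all SAEs, plus reports of those that are related, life-threatening or fatal. Section 6.13 limits what reaches the PSC and Sponsor to related SAEs. Under section 6.13.1 an unrelated fatal event would generally not reach the Sponsor at all, apart from an initial report sent before causality has been assessed. These passages must be reconciled.

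This is a low-cost improvement to oversight that should be made. It does not threaten the feasibility results.

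**What to change.** 1. In the PSC section, replace the annual default for the feasibility study. The Sponsor or the trials unit forwards to the PSC chair, on receipt, each related SAE report and any life-threatening or fatal SAE report that the Sponsor receives, with follow-up information.
2. Fix one short PSC safety review, by email or call, inside the exposure period. Around the close of recruitment (month 4.5) is reasonable: on even recruitment about 15 to 24 of the 40 intervention participants would have finished the programme and 16 to 25 would not. A review when half are randomised (month 2.25) would be too early: at most (2.25 − 1.84)/4.5 = 9% of intervention participants, about 4 of 40, would have finished.
3. In section 10.5, state that this is how SAEs are monitored during the study, and by whom.
4. Make the PSC section and sections 6.13 and 6.13.1 agree on which SAEs are reported to the Sponsor and which reach the PSC.

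The cost is a wording amendment, forwarding of forms that already exist, and one brief remote review by a committee already in place. The downside is slightly more work for the PSC and the trials unit.

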1. BACKGROUND

There is a growing burden of multimorbidity (presence of >2 long term conditions (LTCs) within an individual) (1) due to increasing life expectancy among those with chronic conditions. Importantly, data indicates that there is a relatively higher mortality risk in younger individuals (2) and increased prevalence in deprived areas. (3)

Multimorbidity is associated with a reduced health-related quality of life (HRQoL), functional decline, increased mortality and increased healthcare utilisation, including emergency admissions. (2–6) There is a paucity of effective interventions for multimorbidity (7-9) particularly those with a focus on minimising functional decline and supporting self-management of complex health problems. Rehabilitation, 'the action of restoring someone to health or normal life illness' remains a core component of health service provision. Addressing the unmet rehabilitation need is a global priority. (9)

A substantial body of evidence has demonstrated improvements in functional capacity and HRQoL and reduced hospital admissions following structured exercise-based rehabilitation for several single LTCs including chronic obstructive pulmonary disease (COPD), post-myocardial infarction/revascularisation, heart failure, peripheral vascular disease, chronic renal disease, transient ischaemic attacks, and osteoarthritis. (11-16) The format of these programmes is remarkably similar: commonly extend over 8-12 weeks and comprise of individually prescribed and supervised exercise alongside symptom management and self-management support. However, the current delivery of exercise-based rehabilitation programmes is fundamentally limited in two important ways:

- (1) Provision is dominated by services targeted at cardiovascular and pulmonary conditions, with little or no availability for other LTCs.
- (2) Existing rehabilitation programmes are single disease in focus and not designed to consider the complex health needs of people living with multimorbidity. Furthermore, the workforce are specialists in cardiovascular or pulmonary rehabilitation are not necessarily equipped to manage rehabilitation needs for other long-term conditions or indeed to cope with the co-occurrence of multiple conditions. Therefore, patients with multiple LTCs (alongside their cardiac or respiratory disease) do not benefit fully from a single disease focused programme as they have more complex needs spanning multiple conditions.

We propose an innovative integrated approach to rehabilitation that provides equity of access for people with multimorbidity, and includes a structured programme of supervised exercise training, complex health needs assessment (including medication review), and self-management support of common symptoms spanning different LTC: Personalised Exercise Rehabilitation FOR people with Multiple LTCs (PERFORM) intervention.

1.1 Rationale

Access to exercise-based rehabilitation was identified as a priority by our patient and public involvement (PPI) representatives. The term 'multimorbidity' was unpopular and our group requested we change this throughout the application to 'people living with multiple LTCs', which is the term we will use hereafter, wherever possible. People living with multiple LTCs experience an accumulation of symptom and treatment burden (the workload of self-management) (14) and increasing disability. (16)

Single disease-based care which is not person centred or efficient. Participants in cardiac (CR) and pulmonary rehabilitation (PR) experience important benefits; a reduction in symptom burden, improved physical capacity and enhanced HRQoL for those with these candidate conditions (10,11,17) CR and PR are also cost effective (18,19) and a target growth area in the NHS-England Long Term Plan. (20) Our innovative approach extends the scope of rehabilitation, spreading positive health gains more widely to people managing multiple LTCs, extending beyond those with either a cardiac or respiratory LTC. The development and implementation of a PERFORM intervention will: target the long-term burden of chronic illness, provides more equitable access to health care system rehabilitation for a broad range of LTCs, and importantly be person centred with the potential to improve the health and well-being of more people.

1.2 Review of existing evidence

LTCs are the main challenge facing the health care system in the UK and around the world. LTCs are conditions for which there is currently no known cure, and which are managed with drugs and other non-pharmacological treatments, for example: conditions such as diabetes, cardiovascular disease, chronic renal disease, COPD, arthritis, peripheral vascular disease and inflammatory bowel disease and importantly mental health conditions including anxiety and depression. About 15 million people in England have a LTC (21). Those living with multiple LTCs need a broader approach, than the current single disease focused delivery that dominates health service delivery. The use of many services to manage individual diseases can result in duplication of effort as many LTCs require attention to the same lifestyle factors and is therefore inefficient. Unsurprisingly, current approaches are onerous for patients because of poor coordination and integration, and result in fragmented care which increases treatment burden for the individual.

Multimorbidity is regarded a major global health challenges and identifying clusters of common conditions and their determinants is a key research priority based on a key policy report from Academy of Medical Sciences. (22) The prevalence of difference clusters of LTCs has been studied with a recent systematic review describing 51 studies that examine the prevalence of LTC clusters. (23) However, all the included studies involved cross sectional analysis and did not examine the influence of different clusters of LTCs on HRQoL or adverse health outcomes. Secondly, the numbers of LTCs considered in the included studies for defining multimorbidity clusters were quite limited, with a median of 16 LTCs. A recently published large community study in UK defined multimorbidity clusters in different age groups and compared the risk of mortality and health service use. (24) However, this study did not examine the impact of wider demographic, social and lifestyle factors on multimorbidity clusters and differences in quality of life across various clusters. While a study from Denmark investigated differences in HRQoL for various multimorbidity clusters in their population, their study was very limited, considering only 15 LTCs in defining multimorbidity clusters (25). In summary, there is an evidence gap in research of relationship of multimorbidity clusters with adverse healthcare outcomes and HRQoL, particularly studying the impact of wider sociodemographic, lifestyle and function measures on multimorbidity clusters and using a comprehensive list of LTCs in defining multimorbidity clusters.

The recent update of the Cochrane Review of interventions for multimorbidity (personal communication SuS, submission date planned 2020), includes a total of 29 randomised controlled trials (RCTs) focusing on either specific combination of two health conditions (e.g., cardiac disease and diabetes) or a broader range of conditions and tended to focus on elderly

people. Whilst all interventions involved multiple components, they could be divided broadly into either organisational interventions (e.g. case management or addition of a pharmacist to the clinical care team) or patient-oriented interventions (e.g., self-management support groups or community-based diet and physical activity programmes). Meta-analysis of the RCTs results, showed little or no differences compared to best usual care in outcomes, including clinical measures (e.g., blood pressure, glycaemic control), HRQoL, level health service use and medication use. However, none of these trials appeared to be based on a model of personalised rehabilitation for people with multiple LTCs and did not have a prominent component focusing on restoring exercise performance and functional capacity thus reducing the individuals' level of disability associated with LTCs. The authors of this Cochrane Review proposed that interventions that focused upon physiotherapy treatments that aimed to improve functional capacity to support physical activity and achievement of activities of daily living may be more effective, but there was a need for further studies with this type of intervention particularly for people living with multiple LTC's across a range of ages (7). Despite this Cochrane Review recommendation, there is very limited RCT evidence to date reporting this type of exercise intervention in the literature, which should be personalised, prescribed and progress on an individual basis for people with LTCs (see below). In summary, there is a lack of data describing effective and cost-effective interventions for those with multiple LTCs, (7,8) making this global health challenge a key research priority.(9)

